3.0 OBJECTIVES AND ENDPOINTS

3.1 Study Overview

We will test the ATVV, a multisensory behavioral intervention, where mothers learn to engage with their infant while administering Auditory (infant directed speech), Tactile (massage), Visual (eye to eye gaze), and Vestibular (rocking) stimulation.⁽²⁴⁾ We build on ATVV's success with preterm infants and their mothers (e.g., improved maternal sensitivity, lower maternal distress, and enhanced infant behavior and development) to determine benefits for full-term M-I dyads.⁽²⁵⁻³⁰⁾ We will target first-time mothers with childhood adversity. Mothers randomized to ATVV will administer it once daily for the first 3 postnatal months. At 3 months, when full-term infants reliably exhibit clear cues and maintain alertness, we will apply a rigorous behavioral measure of M-I synchrony developed by a member of our team using frame-by-frame video of micro-coded M-I behavior quantifying reciprocal speech, touch, gaze, and affect.^(31, 32, 73) Micro-coded behavior yields rich detail of interaction patterns known to influence long-term developmental outcomes.^(7, 18, 19) Our feasibility pilot showed significant and strong correlations between ATVV frequency and improved M-I synchrony over one month.

We will also assess ATVV's effect on maternal and infant peripheral OXT levels,^(7, 19) a known biomarker of M-I synchrony. We, and others, have shown that dampening in the OXT system (i.e., abnormally low OXT blood and saliva levels) is evident in poor M-I synchrony and maternal behavior,⁽³³⁻³⁷⁾ yet little is known about OXT's epigenetic regulation of synchrony or maternal behavior in humans. Thus, we will target regions of the **OXT receptor gene (OXTR)** where DNA methylation is linked to maternal behavior in rodents, psychosocial behaviors in humans, and in our pilot study to M-I synchrony.⁽³⁸⁻⁵²⁾ We will examine whether our OXT measures emerge early to predict efficacy of ATVV and quality of M-I synchrony at 3 months. We analyze maternal blood in pregnancy and at 1, 2, and 3 months post birth (and infant salivary OXT). We aim to identify molecular mechanisms in the OXT system underlying M-I synchrony in maternal blood and discover molecular profiles. Regression based methods assess ATVV effects on and relations among M-I synchrony and OXT measures.

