4.2 ATVV Intervention

4.2.1 Description of ATVV Intervention

The ATVV (Auditory, Tactile, Visual, Vestibular stimulation) is a 15 minute multisensory behavioral intervention consisting of infant-directed affectionate "motherese" speech, moderate touch massage, eye to eye gaze, and horizontal rocking.^(24, 76, 77) The ATVV intervention provides clinicians a low-cost, easily accessible intervention for mothers to implement that has been well researched by our team with preterm infants.⁽²⁵⁻³⁰⁾ The Pathways Foundation, whose educational materials are approved by the American Academy of Pediatrics, includes ATVV in their education for parents with preterm infants (<https://pathways.org/growth-development/massage-30-10-5/>). ATVV is an enjoyable daily opportunity for mothers to practice modeling M-I synchrony by using eye to eye gaze, affectionate speech and soothing touch.

During the 15-minutes in which ATVV is administered, multisensory stimuli are presented in gradual progression:^(24, 76, 77) "motherese" speech which is infant-directed speech typically high-pitched with a sing-song rhythm for 30 seconds, followed by massage for 10 minutes, with eye to eye gaze added as the infant becomes alert (ideally at the beginning of the intervention), and ending with rocking for the remaining 5 minutes. Importantly, "motherese" is maintained throughout the entire 15-minute intervention as long as disengagement cues are not exhibited. M-I engagement is attempted throughout the intervention; thus, mothers learn to identify, interpret and adapt to their infant's developmentally appropriate cues. The ATVV is applicable throughout the study period because it can be given even if the infant is too young for eye to eye gaze. Regardless of whether the infant is 1, 6, or 12 weeks old, ATVV is always offered contingent on infant cues to promote self-regulation and is withdrawn if the infant exhibits persistent disengagement cues.^(24, 76)

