4.2.2 Administration of Intervention

ATVV is administered by mothers soon after birth,^(29, 30, 78) thus, filling a gap for simple interventions to promote engagement between mother and infant in early infancy when experience-dependent neural plasticity is high in maternal and infant brains.^(22, 23) In administering ATVV, mothers learn to be comfortable recognizing and adapting their behavior when the infant is signaling cues to engage or disengage. ATVV is an enjoyable daily opportunity for mothers to practice modeling M-I synchrony by using eye to eye gaze, affectionate “motherese” speech and soothing touch.⁽⁷⁸⁾

Mothers will be instructed to administer ATVV for 3 months, once daily at any time of their choosing, as long as it is in-between feedings when the infant is ready to interact but not too hungry (resulting in fussiness) and not too full (resulting in sleepiness). Daily use allows for ATVV to frequently reinforce positive M-I interaction. While twice versus once daily (in comparison to controls) yields more significant improvements in biologically at-risk preterm infants,^(23, 27, 29, 30) our pilot showed that once versus twice daily is more acceptable for mothers of healthy full-term infants. A research team member will teach the intervention with the assistance of the ATVV Intervention Manual for Parents, and the online ATVV teaching video targeting newborns. The ATVV is easily learned within one hour and shown to be highly acceptable by mothers in the literature and in our pilot (> 90% agreement with the ATVV Reliability Checklist).⁽⁹⁷⁾ In addition to taking home the ATVV manual, mothers can access our online teaching videos with infants at three different ages (newly born, 6 weeks, and 3 months old).

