4.3 Intervention Compliance

To monitor mothers' fidelity and dosage of ATVV once daily, we will use text messaging through Twilio, an electronic communications platform within REDCap. To have access to a phone capable of text messaging is an inclusion criterion to participate in the study. Participants may tire of responding to daily texts, but our daily text is extremely brief requiring only a keystroke to respond. If a phone becomes lost, we will provide a temporary one. Each evening, Twilio will text the following-

- Please tell us how many minutes you gave your baby the Massage Plus today. Choose between 0-15 minutes.
- Please tell us the level of stress you may have experienced today on a scale of 0-10.

The question on stress is included because the attention-control mothers also receive the identical text message and stress is a covariate. See section 4.5. We will monitor REDCap daily, and call mothers if we identify noncompliance two days in a row. Second, we will ask during the weekly phone calls if anyone else besides the mother gave the massage. At each weekly phone call and monthly study visit, we will review how often mothers use the intervention (self-report vs REDCap data) and discuss solutions to barriers of fidelity (e.g. lack of time, fussy or sleepy infant). We will also discuss who else may be giving the massage to their baby.

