4.8.1 Evaluate Efficacy of ATVV

Aim 1: Evaluate the efficacy of daily ATVV among mothers with childhood adversity on behavioral and physical measures of M-I synchrony in a randomized study with an Attention Control group. The goal of our analysis is to determine treatment arm differences at the study endpoint (3 postnatal months), using a 2.5% type I error rate and two-sided test for our primary outcomes. We will use 5% type I error rate and Benjamini Hochberg correction among related groups of secondary outcomes.⁽¹⁴⁷⁾ We will estimate treatment effects with and without key covariates known to be associated with M-I synchrony (e.g., mental health, adversity, infant feeding method, infant health status, and 1-month Parenting Stress Index) which will increase the power of the test. For infant outcomes, we will include sex as a covariate and test for treatment effect differences by sex using an interaction term. Our statistical method for the physical measures, measured at baseline (late pregnancy) and monthly intervals (1-, 2-, and 3- postnatal months), will be MMRM regressing the outcome on indicators for treatment, time, and their interaction. For the physical measures the goal is to determine treatment arm differences in change from baseline to the study endpoint. In contrast, our method for the behavioral outcomes, measured once at the study endpoint, will be a general linear model regressing the outcome on an indicator for treatment arm. We will conduct intention to treat (ITT) and per protocol analyses (defined as completing 80% or more of daily ATVV sessions) and compare our findings. While missing data will be minimized through careful procedures, some missing data are inevitable with longitudinal studies. In order to retain all randomized participants for ITT, we will use multiple imputation to predict missing outcomes with all available measures, and model aggregated results across imputation datasets.⁽¹³⁸⁾ For physical measures where we have repeated measurements, we will compare multiple imputation results to the full information maximum likelihood approach available through MMRM. We will use inclusive models with auxiliary variables related to missingness, among covariates collected at baseline, if needed to support the missing at random assumption.^(138, 139) Sensitivity analyses will assess the robustness of our findings if we find imbalanced baseline characteristics in spite of randomization, characteristics associated with attrition, or non-ignorable missing data. We will conduct fidelity and dose response analyses in addition to our main effects models. Dose (frequency of ATVV sessions) will be collected daily for three months from the treatment arm participants and can be used to explore the patterns of adherence over time as well as optimal dose associated with OXT system changes by month.

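### The exploratory search for an optimal ATVV dose uses self-selected dose variation within one arm, so it cannot identify an optimum and may show a dose-oxytocin association when ATVV has no effect

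*Combined protocol and SAP*

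**What the plan says.** Section 4.8.1 commits to this work beyond the randomised comparison: "We will conduct fidelity and dose response analyses in addition to our main effects models". The data come from one arm: "Dose (frequency of ATVV sessions) will be collected daily for three months from the treatment arm participants". The stated use is that they "can be used to explore the patterns of adherence over time as well as optimal dose associated with OXT system changes by month".

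Section 4.2.2 assigns one schedule to the whole arm: "Mothers will be instructed to administer ATVV for 3 months, once daily at any time of their choosing". It also asks mothers to choose a moment between feeds when the infant is ready to interact. Section 4.2.1 adds that "ATVV is always offered contingent on infant cues to promote self-regulation and is withdrawn if the infant exhibits persistent disengagement cues". Section 4.3 has staff "discuss solutions to barriers of fidelity (e.g. lack of time, fussy or sleepy infant"), and it records dose as self-reported minutes from 0 to 15 in a nightly text. Section 4.8.1, by contrast, defines dose as session frequency.

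The documents give no model, time ordering or covariate set specific to the dose analysis, and no statement that it is to be read as association only.

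**The concern.** An optimal dose is a causal quantity: the amount that would give the best result if mothers were assigned to it. Only one amount is assigned here. Differences in delivered dose within the ATVV arm are missed or shortened sessions, and randomisation does not protect comparisons among them.

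The plan itself names reasons why delivered dose may follow the dyad's state: readiness to interact, fussiness, sleepiness and, for minutes, disengagement. Section 2.1.7 reports that more synchronous dyads have higher oxytocin in parent and infant. A trait such as an easily engaged infant could therefore raise both dose and oxytocin. Relating the two month by month, with no stated time order, also leaves room for the outcome process to influence the dose.

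At stake is how a secondary analysis is read. Section 4.2.2 already weighs once against twice daily use, and Section 3.1 cites a pilot association between ATVV frequency and synchrony. An optimal-dose finding would speak to a question the team has open, and calling it exploratory does not remove the bias.

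**Working it through.** **The plan's own figure.** Section 4.7 gives 80% power for a 0.44 SD difference with 100 per arm and two-sided alpha 0.025. Check: 0.44 × √(100/2) = 3.111; 3.111 − 2.241 = 0.870; Φ(0.870) = 0.808. It reproduces. It concerns the randomised contrast, and no figure is given for the dose analysis. What carries over is n = 125 × 0.80 = 100 ATVV dyads.

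**Set-up.** Suppose ATVV has no effect. A dyad trait U has correlation a with dose and b with oxytocin change. The documents give neither value, so both are assumptions. The dose-outcome correlation produced by U alone is r = a × b.

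**Chance of p<0.05 (two-sided, Fisher z).** m = atanh(r) × √(n − 3), with √97 = 9.849. Probability = Φ(m − 1.96) + Φ(−m − 1.96).

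| a = b | r | m | Chance of p<0.05 | Simulation (20,000 replicates) |
|---|---|---|---|---|
| 0.2 | 0.04 | 0.394 | 6.8% | 7.0% |
| 0.3 | 0.09 | 0.889 | 14.4% | 14.6% |
| 0.4 | 0.16 | 1.589 | 35.6% | 35.7% |
| 0.5 | 0.25 | 2.516 | 71.1% | 71.5% |

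With a = 0.3 and b = 0.5 the simulated rate is 32%. With a = 0, so that dose does not depend on the trait, it is 4.9%. Adjusting for U measured without error returned 4.8% to 5.1% in every setting. A simulated two-arm randomised comparison under no effect gave 5.0% to 5.1%.

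**If collected covariates capture part of the trait.** Suppose they carry half of U's variance (also an assumption). The partial correlation for a = b is (a²/2) / (1 − a²/2).
- 0.3: 0.045/0.955 = 0.047
- 0.4: 0.080/0.920 = 0.087
- 0.5: 0.125/0.875 = 0.143

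With √96 in place of √97, the rates are 7.5%, 14% and 29%. Adjustment helps but does not restore 5%.

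**Which dose is exposed.** Withdrawal on disengagement (4.2.1) shortens a session already begun, so it acts mainly on minutes. Readiness to interact (4.2.2) and the fussy or sleepy infant (4.3) can also affect whether a session happens, and so frequency. Both measures are exposed, by different routes.

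**The case against.** **The analysis is labelled exploratory, sits beside the main models, and is not an aim or hypothesis in Section 3.2.** This stands. A reader might infer that the efficacy conclusion is at risk, or that a dose will be recommended from this analysis. The documents support neither: the intention-to-treat comparison does not use dose, and no section promises a recommendation.

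**Adjustment is not absent from the plan.** This stands in part. Section 4.5 makes a general commitment to control for the Table 3 covariates, which include depressive symptoms, anxiety, adversity and the Parenting Stress Index short form (PSI-SF) with its difficult-child domain. Section 4.3 treats daily stress as a covariate. So it would be wrong to infer that nothing is planned. What is missing is how any of these enter the dose model, and at what time point. The covariate list in 4.8.1 is given for treatment effects.

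**The link from engagement to frequency is weaker than it looks.** This stands in part. Mothers choose the time of day, so a fussy spell can be waited out; lack of time is also a named barrier; and two noncompliant days prompt a call. Some dependence on infant state remains plausible, but the text does not show that infant engagement governs session frequency.

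**Size and direction are assumed.** This stands. At correlations of 0.1 the rate is 5.1%. Section 2.1.7 links synchrony to oxytocin levels, whereas the outcome here is change, in which stable differences partly cancel. A reader might infer a bias towards more being better, since the pilot reported "Our feasibility pilot showed significant and strong correlations between ATVV frequency and improved M-I synchrony over one month". The documents do not establish that. Section 2.1.6 describes ATVV as soothing, so mothers of fussy infants might use it more, and nothing shows that the pilot result was confounded.

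**Conclusion.** The concern holds in a limited form. With one assigned schedule and dose observed in one arm only, the planned analysis cannot identify an optimal dose, whatever the sample size. It may also show an association between dose and oxytocin when ATVV does nothing, because part of the variation in dose plausibly follows infant state.

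The inflation is unknown. It runs from about 7% to 71% for trait correlations of 0.2 to 0.5 with both dose and outcome, 100 dyads, one marker and no adjustment. It is less to the extent that collected covariates capture the trait. Those correlations are assumptions, and the direction of bias is open. The randomised result stands untouched, so this is a correction to a secondary analysis that should be made, not a flaw in the trial's main inference.

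**What to change.** In Section 4.8.1:

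1. Remove optimal dose as an aim or possible conclusion, and state that the dose analysis is reported as association only.
2. Name one dose measure, reconciling session frequency (4.8.1) with self-reported minutes (4.3).
3. Relate oxytocin measures at each visit to dose in the preceding interval. Adjust for the same measure at the prior visit and for baseline depressive symptoms, GAD-7, ACE score and baseline oxytocin.
4. Add infant and maternal state recorded before that interval: prior-visit PSI-SF, including the difficult-child domain, and earlier daily stress texts. By the Section 1.4 schedule, PSI-SF and infant saliva start at T1, so the interval from birth to T1 has only prenatal maternal measures to adjust for. Say so. State also that postnatal measures may themselves be affected by ATVV.
5. Optionally, add a sensitivity analysis with randomised arm as the instrument for dose received. State its assumptions: arm acts only through ATVV delivered, the effect is linear in dose, and control exposure is measured or taken as zero. The first is debatable, because the training itself teaches mothers to read cues. The estimate is the arm difference in outcome divided by the arm difference in mean dose. It is an average effect of dose received and says nothing about the shape of a dose-response.

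The cost is SAP wording and modest analysis of data already scheduled. The optimal-dose claim is given up, and residual confounding remains because infant engagement is captured only by proxy.

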
4.8.2 Identify OXT-System Mechanisms Associated with M-I Synchrony

Aim 2: Identify molecular mechanisms in the OXT system underlying M-I synchrony. We will examine the time change pattern of OXT elements to understand the form of their trajectory (e.g., ascending or descending, linear, quadratic) using locally weighted regression (lowess) graphs, stratified by treatment arm. We will also assess the form of hypothesized relationships between elements (i.e., *OXTR* methylation negatively related to *OXTR* mRNA, OXTR protein, and OXT peptide - which are positively related to each other) stratified by treatment group and time. We will model these time change patterns with MMRM and use interactions of time, intervention, and the OXT element to establish if aspects of the OXT system and/or their interrelationships change over time and if that change is influenced by the ATVV intervention. Ultimately, we will assess if the behavioral measure of M-I synchrony is associated with the OXT system and its components, including methylation at base pairs and time trends across repeated measurements. We will examine covariates such as childhood adversity and cumulative stress for their substantive contribution to understanding the relationship between M-I synchrony and OXT functioning, including effect modification with interaction terms. While we will test for heterogeneity in random coefficients through MMRM, we will further explore population heterogeneity using bioinformatics methods, described below, which will provide a complementary, person-centered approach to understanding how subgroups inferred from the OXT indicators are related to personal characteristics, dose, and outcomes.

Molecular Profiles: To address heterogeneity in molecular profiles we will perform a clustering analysis to identify potential subgroups with differing patterns of associations within the OXT system. We will use k-means clustering, doing a search for the optimal number of clusters k by repeating clustering several times for each k over a wide range and using consensus clustering statistics to determine the values of k that yield highly reproducible clustering results. This will yield sample sub-groups that faithfully capture the heterogeneity in the data set without over-fitting clusters to noise. We can then profile the subgroups using the key covariates, treatment arm, and M-I synchrony using descriptive and bivariate inferential statistics. In addition, we can examine the different molecular profiles that discriminate different sub-populations to determine putative molecular mechanisms linked to different outcomes observed in the covariate analysis. We will evaluate such differences both qualitatively, using heatmap visualizations, and quantitatively, based on differences between cluster centroids. This will allow us to generate hypotheses about biomarkers that might distinguish individuals most likely to benefit from the intervention. These combined methods will inform us about the efficacy of the ATVV intervention, increase our understanding of the OXT system associated with M-I synchrony, and support our future research to enhance targeted or tailored intervention efforts.

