3.2 Aims

To meet these objectives, we have designed a 4-year, single-site, randomized, attention-controlled clinical trial with the following aims:

Aim 1: Evaluate the efficacy of daily ATVV over 3 postnatal months among mothers with childhood adversity.

We hypothesize that compared to the Attention Control group (n=125), mother-infant dyads in the ATVV group (n=125) will exhibit:

- H1: Higher oxytocin (OXT) function (i.e., decreased oxytocin receptor (OXTR) gene methylation at candidate sites, and increased OXTR mRNA, OXTR protein, and OXT in maternal plasma, and increased OXT in infant saliva) at 1, 2, and 3 postnatal months.
- H2: More synchronous eye-to-eye gaze [primary], positive affect [primary], speech, and touch at 3 postnatal months.

Aim 2: Identify molecular mechanisms in the OXT system underlying mother-infant synchrony (N=250).

- H1: We hypothesize that lower mother-infant synchrony will be associated with dampening of the OXT system, evidenced by increased OXTR methylation at candidate sites, and decreased OXTR mRNA, OXTR protein, and OXT in maternal plasma, and decreased OXT in infant saliva at 3-postnatal months.

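### Section 4.8.2 does not say whether the repeated-measures links between OXT elements are between mothers or within a mother; a single-term predictor would blend the two.

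*Combined protocol and SAP*

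**What the plan says.** Section 4.8.2 expects OXTR methylation to be negatively related to OXTR mRNA, OXTR protein and OXT peptide, and the last three to be positively related to one another. These relations are first inspected by arm and time point. The plan then moves to an MMRM and will "use interactions of time, intervention, and the OXT element to establish if aspects of the OXT system and/or their interrelationships change over time", and will also ask whether ATVV influences that change. No model equation is given. The text does not say which element is outcome and which is predictor, or how the predictor is centred.

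Section 4.8.1 supplies the sampling scheme. The method for the physical measures, "measured at baseline (late pregnancy) and monthly intervals (1-, 2-, and 3- postnatal months), will be MMRM". Each mother therefore has up to four values of every blood measure, and an element used as a predictor varies over time.

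Two further statements set the limits of this point. Section 4.8.2 adds, "While we will test for heterogeneity in random coefficients through MMRM", that clustering will explore heterogeneity further. Section 4.8.1 says that "our method for the behavioral outcomes, measured once at the study endpoint, will be a general linear model", so synchrony has one value per dyad.

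**The concern.** Two different statements can lie behind a correlation between, say, methylation and mRNA in repeated samples. One is between mothers: those with higher average methylation have lower average mRNA. The other is within a mother: when her methylation falls, her mRNA rises. A mixed model with the element as one term returns a precision-weighted average of the two slopes.

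The proposed action of ATVV is a change over time: the massage is to alter epigenetic regulation and so OXT function. The within-mother slope speaks to that. The between-mother slope can come from any lasting difference between mothers, and the protocol's premise (Section 1.1) is that childhood adversity dampens the OXT system for the long term. Correlated stable levels across several elements are therefore plausible in this population. Aim 2 is framed as identifying molecular mechanisms, so a blended coefficient could be reported as evidence that the elements move together when only stable levels are correlated.

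The tools already in the plan do not settle this. Looking at relations by arm and time point is cross-sectional. Random-coefficient tests and clustering address heterogeneity, not the separation of the two slopes.

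**Working it through.** **The plan's only Aim 2 figure.** Section 4.7 gives 80% power for a correlation of 0.22 at alpha 0.01. By Fisher's z, power = Φ(atanh(r)·√(N−3) − z), with atanh(0.22) = 0.2237.
- N = 200: 0.2237 × 14.04 = 3.139. One-sided, Φ(3.139 − 2.326) = 79.2%. Two-sided, Φ(3.139 − 2.576) = 71.3%.
- N = 250: 0.2237 × 15.72 = 3.515. One-sided 88.3%, two-sided 82.6%.

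The figure reproduces most closely with N = 200, one-sided; the plan states neither the N nor the sidedness for it. It refers to a simple correlation. There is no figure for the MMRM coefficient, so its behaviour has to be worked out.

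**Inputs.** From the documents: 200 mothers at the endpoint (Section 4.7), four visits (Section 4.8.1), alpha 0.01 (Section 4.7). Assumed: ICC 0.5 to 0.7, between-mother correlation r of 0.3 to 0.5 in absolute value, no within-mother link, complete data. The sign of r does not matter.

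**Closed form.** Give both elements variance 1 and ICC ρ.
- Slope between mother means: β_B = rρ / [ρ + (1−ρ)/4]. Within-mother slope: β_W = 0.
- Information per mother: W_B = 4·Var(mean X)/V_B and W_W = 3(1−ρ)/V_W. V_B is four times the residual variance of the mother means, and V_W is the within-mother residual variance.
- Single-term coefficient: b = (W_B·β_B + W_W·β_W)/(W_B + W_W). Standard error: 1/√[200(W_B + W_W)].

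For r = 0.5 and ρ = 0.5:
- β_B = 0.25/0.625 = 0.40.
- V_B = 4 × (0.625 − 2 × 0.1068 × 0.25 + 0.1068² × 0.625) = 2.315. V_W = 0.5 + 0.1068² × 0.5 = 0.506. (b = 0.1068 is the solution reached by iteration.)
- W_B = 2.5/2.315 = 1.080. W_W = 1.5/0.506 = 2.966.
- b = 0.40 × 1.080/4.046 = 0.107, although the true within-mother slope is 0.
- Standard error = 1/√(200 × 4.046) = 0.0352, so z = 3.04. Probability of significance at two-sided 0.01: Φ(3.04 − 2.576) = 68%.

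**Closed form against simulation, alpha 0.01, no within-mother link.** The simulations used random-intercept or unstructured covariance.

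| Between-mother r | ICC predictor / outcome | Closed form | Simulated |
|---|---|---|---|
| 0.3 | 0.5 / 0.5 | 20% | 18%, 22.5%, 24% |
| 0.5 | 0.5 / 0.5 | 68% | 65%, 67%, 67% |
| 0.3 | 0.7 / 0.7 | 27% | 26.5% |
| 0.5 | 0.7 / 0.7 | 82% | 77%, 81% |
| 0.3 | 0.7 / 0.5 | 43% | 41% |
| 0.5 | 0.7 / 0.5 | 96% | 93% |

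After the split, the deviation term rejects in about 1% of runs at alpha 0.01 and in 4% to 7% at alpha 0.05. With no between-mother correlation the single term rejects in about 6% at alpha 0.05, so the excess comes from stable differences between mothers.

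**The interactions that 4.8.2 names, nominal 5%, no within-mother link.**
- Element-by-arm and element-by-time-by-arm stay near nominal with the single term, at about 5% to 7% in every variance pattern tried.
- Element-by-time is 6% to 8% when variances are constant over visits.
- If between-mother variance is smaller in pregnancy than after birth, element-by-time rises. The size depends on the imbalance: 20% to 26% in strongly unequal patterns, 8% to 13% in milder ones.
- In the strongly unequal patterns, splitting the element and letting both parts vary by visit brings element-by-time to 5% to 6%. In milder patterns at ICC 0.7, interactions on the deviation alone leave 10% to 11%, against 5% to 7% when both parts carry them.

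**The case against.** Four objections have force.

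- **The single term is inferred.** Section 4.8.2 gives no equation. The defect is an unstated decomposition, not an explicit wrong model. This stands. It still leaves the choice open until data are in hand, and one term is what most analysts would fit from that text.
- **The large error rates are for the element's own coefficient, while the section speaks of interactions.** This also stands. A reader might infer that the test of whether ATVV alters the relation between elements is biased. The simulations do not show that: the arm interactions stay near nominal. Element-by-time is inflated only under the added assumption that between-mother variance differs by visit.
- **Between-mother association is part of what Aim 2 asks.** Section 3.2 states, "We hypothesize that lower mother-infant synchrony will be associated with dampening of the OXT system". Because synchrony is measured once, that hypothesis is necessarily between mothers and cannot be split. A reader might infer that only within-mother slopes matter to Aim 2, or that H1 is invalid. The documents support neither.
- **Aim 2 is exploratory in part, and the ICCs and correlations are assumed.** True. Rates near the top of the range need a correlation of 0.5 and a high ICC for the predictor.

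A reader might also argue that opposite-signed slopes could cancel and hide a real within-mother link. That is possible in principle, but the plan hypothesises one direction for each pair, so nothing in the documents points to it.

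**Conclusion.** The point holds for the element-to-element MMRM in Section 4.8.2. If the predictor is entered as one term, its own coefficient cannot be read as change tracking change. With no within-mother link it would be significant at alpha 0.01 in roughly 20% to 90% of trials, for between-mother correlations of 0.3 to 0.5 and ICC 0.5 to 0.7 with 200 mothers. At a correlation of 0.22 and ICC 0.3 to 0.7, simulated rejection at alpha 0.05 was 16% to 30%. The ICCs, correlations and complete data are assumptions; the direction of the problem does not depend on them, provided stable levels are correlated at all. Element-by-time shares the problem only if between-mother variance changes over visits. The primary outcomes, the sample size, Aim 2 H1 and the arm interactions are outside this conclusion. It is a worthwhile and cheap improvement to a secondary analysis, not a threat to the trial's efficacy result.

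**What to change.** In the Section 4.8.2 element-to-element MMRM:

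1. State for each model which element is outcome and which is predictor.
2. Replace each time-varying predictor element by two terms: the mother's mean over her available samples, and the visit-specific deviation from that mean.
3. Give both terms their own time and intervention interactions. Putting them on the deviation alone does not fully repair element-by-time.
4. Report the two associations separately. Base statements about within-mother change, the mechanism proposed for ATVV, on the deviation terms. Label the mother-mean terms as between-mother associations.
5. Say that the association of synchrony with OXT is between mothers by design, so that it is not read as change within a mother.

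The cost is SAP wording, two derived variables per predictor element (the mean and the deviation) and a few more parameters. No new data are needed. If the two associations are in fact equal, the split loses some power: at a correlation of −0.15 and ICC 0.5, from about 93–97% to about 84–89%.
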